### **Statistics and Analysis**

This randomized controlled trial will enroll consecutive patients and randomizing one eye to control treatment and the other eye to the experimental treatment. Assuming a mean pain score of 3.5 with standard deviation of 1.6 for control treatment, we need to enroll 30 patients and randomize one eye to control and one to experimental treatment to detect a mean difference of one score in pain with beta of 0.1 (90% power) and alpha of 0.05 (significance level of 0.05) if the null hypothesis of no difference in population means is true.

Baseline characteristics will be summarized as frequencies and relative frequencies for categorical data and mean and standard deviation for continuous data. Paired t-test will be used to compare the pain score between control and experimental eye and mean difference with 95% confidence interval will be reported as treatment effect. For categorical outcome measure, McNemar test will be used for comparison between control and experimental eye and proportions will be reported. A p-value of 0.05 will be set for statistical significance.

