## **Project Summary**

Ptosis (eye lid drooping) can be corrected surgically via a procedure called Fasanella servat. As eyelid tissue is cut and existing edges sutured back together, the sutures can cause some irritation to the eye. Bandage contact lenses are used with the idea that it will protect the cornea by providing a protective layer from the sutures (Fontana, 1978). A study conducted by Awan *et al.* suggests that soft contact lenses may be a beneficial choice in surgeries involving the upper eyelid (Awan, 2009). To truly see any benefits in patients, studying the effects of bandage contact lenses in patients with ptosis surgery is important. Patients who require ptosis surgery on both eyes will be part of the study and one eye will be randomized to receive the bandage contact lens and the other eye will not. Pain/discomfort and blurred vision will be compared between the 2 eyes and the results will help us determine if the use of bandage contact lenses is warranted in ptosis eye surgery. If the lens is found to be unneeded, this can provide significant healthcare cost savings and prevent unnecessary resource utilization. Moreover in terms of the patient experience, if the lens is unneeded, this can provide a more comfortable recovery period (no hassles with keeping the lens in place) and any unnecessary complications by having a lens on the eye (i.e. blurred vision, foreign body sensation, etc.). Bandage contact lenses have been demonstrated to have reduced discomfort; however, patients had a preference not to wear them during the later parts of their recovery time as they did not experience much in terms of blurred vision and discomfort (Ahmed et al, 2001). Moreover, in a study by Shimazi *et al.* with corneal transplantation, it was concluded that no significant benefits were observed through the use of bandage contact lenses in their patients (Shimazi et al, 2016). Based on the above, it is hypothesized that the bandage contact lenses will not have a major impact on the pain/discomfort that the patient experiences and likely will not need to be routinely used.

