## **Methods**

**Participants:** The study population will include patients who have bilateral ptosis (drooping eyelids) and will require surgery to correct this, patients in this study will have no other eye related pathologies. In general, patients are older than 50 years old and from any demographic.

**Design and Procedure:** In this randomized control trial, 30 patients requiring surgery (Fasanella Servat procedure) with bilateral ptosis will have one eye randomized to receive a bandage contact lens whereas the other eye will not after their surgery. Participants will have a random number assigned in order to anonymize data and protect patient identity. We will place a contact lens on both eyes and immediately take it off from one (this will be the sham lens eye). Randomization of the lens placement will be determined by a flip of a coin (heads – keep lens on right eye. Tails – keep lens on left eye). Investigator will randomly generate for each patient whether the contact lens will be kept on right or left eye, sham contact lens will be placed on other eye, placing it and immediately removing it. Therefore, the patient will not know which eye has a lens. Follow up will occur in one week after their surgery where the outcomes will be obtained through questionnaires. Upon 1 week follow up, the person administering the questionnaire is also blinded as they will not know which eye was randomized to have the lens placed. The primary outcome that will be obtained during the study is the patient's pain/discomfort. This will be obtained using the Eye Sensations Scale where the patient can select a box from None, Mild, Moderate, Severe, to Extreme. The secondary outcome that will be obtained is to determine if the patient has experienced blurry vision. This will be measured using one question from the Ocular Surface Disease Index (OSDI), with a scale from 0 (none of the time) to 4 (all of the time).

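### The plan hypothesizes no major impact on pain but tests only zero difference, and does not say how the planned 95% CI and the 1-point target bear on that hypothesis

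*Combined protocol and SAP*

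**What the plan says.** The Project Summary sets out what the trial hopes to support: "it is hypothesized that the bandage contact lenses will not have a major impact on the pain/discomfort that the patient experiences". It adds that "the results will help us determine if the use of bandage contact lenses is warranted in ptosis eye surgery", and describes what follows from a negative finding: "If the lens is found to be unneeded, this can provide significant healthcare cost savings".

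The Statistics and Analysis section sizes the trial at 30 patients, one eye each way, for 90% power to detect a 1-point mean difference at alpha 0.05. The null there is zero difference ("if the null hypothesis of no difference in population means is true"). The inputs are introduced with "Assuming a mean pain score of 3.5 with standard deviation of 1.6 for control treatment". For the analysis, "Paired t-test will be used to compare the pain score between control and experimental eye", and the mean difference with its 95% CI is to be reported as the treatment effect. The only threshold is a p-value of 0.05. McNemar's test is assigned to the categorical outcome, so it is not a second test of the pain score.

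Neither section gives a number for a major impact, calls the 1-point difference a margin, or says which confidence interval would support the hypothesis.

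**The concern.** The hypothesis is that an important effect is absent, while the test asks whether the effect is exactly zero. Failing to reject zero is compatible with no effect, but also with an effect large enough to matter. Conversely, a small benefit can be significant and still not be major. The p-value therefore cannot by itself support or refute the stated hypothesis.

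The 90% power does not close this gap. It limits how often a true 1-point benefit goes undetected. It does not say how to read a particular non-significant result. Without a rule fixed beforehand, whether an ambiguous interval counts towards the lens being unneeded is decided after the data are seen. That judgement would inform whether a lens in current use is dropped.

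**Working it through.** **Inputs from the Statistics and Analysis section.** 30 patients (paired eyes), SD 1.6 (stated for control treatment), difference to detect 1 point, alpha 0.05, 90% power.

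**Assumptions.** The test is two-sided, which fits the 95% CI. Both eyes have SD 1.6. Differences are roughly normal. The plan gives neither the SD of the paired differences nor the between-eye correlation ρ, so ρ is varied: SD of differences = 1.6 × √(2(1 − ρ)). This is 1.13 at ρ = 0.75, 1.60 at ρ = 0.5 and 2.26 at ρ = 0.

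**Step 1: reproduce the sample size.** For a two-sided paired t-test with SD of differences 1.6 and a 1-point difference (noncentral t), 90% power needs 29 patients, and 30 give 91.1%. This matches the plan. At SD 2.26 the number needed is 56, so ρ = 0 does not fit the stated 30.

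**Step 2: width of the interval.** Half-width = t(0.975, 29) × SD / √30 = 2.045 × 1.6 / 5.477 = 0.597. Take the difference as control eye minus lens eye, so that positive values favour the lens. At an observed SD of 1.6, a result is non-significant if the observed difference is below 0.597 in size. The upper limit is at or above 1 if the observed difference is at least 1 − 0.597 = 0.403. Observed benefits of about 0.40 to 0.60 therefore have an interval containing both 0 and 1.

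This overlap needs a half-width above 0.5, that is, an observed SD of differences above 0.5 × 5.477 / 2.045 = 1.34. With equal SDs of 1.6, that means ρ below 1 − (1.34/1.6)²/2 = 0.65.

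**Step 3: how often it happens.** Simulated chance, with 30 pairs, that the result is non-significant and the upper 95% limit is at or above 1:

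| SD of differences (ρ) | True benefit 0 | 0.25 | 0.5 | 0.75 | 1 |
|---|---|---|---|---|---|
| 1.13 (0.75) | <1% | <1% | <1% | <1% | <1% |
| 1.60 (0.5) | 7% | 18% | 25% | 18% | 7% |
| 2.26 (0) | 33% | 50% | 57% | 50% | 33% |

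At SD 1.6 and a true benefit of 0.5, 62% of trials are non-significant, and 0.25/0.62, about 41% of those, still include 1 point.

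**Step 4: what 30 patients can support.** Chance, at zero true difference, of meeting each criterion:

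| Criterion | SD 1.6 | SD 2.26 |
|---|---|---|
| Upper 95% limit below 1 (no major benefit) | 91% | 65% |
| Whole 95% CI within ±1 (no major impact either way) | 82% | 30% |

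At SD 1.6, the one-sided criterion needs 29 patients for 90% power and the two-sided one about 36. Smaller margins for the one-sided criterion give 70% (0.75 points) and 38% (0.5 points) with 30 patients.

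**The case against.** The strongest reply is that no wrong inference is planned. The expectation of no major impact stands in the background summary as a reading of earlier literature. The statistics section sets up a coherent test of difference, and expecting little effect does not turn it into an equivalence trial. The 95% CI is already to be reported, and the 1-point target gives a benchmark against which anyone can read it.

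Much of this stands. A reader might infer that the investigators will treat p > 0.05 as proof that the lens is unneeded, but the documents do not say so. A reader might also infer that there is no benchmark at all, but the 1-point difference is one, even though it is not called a margin. The size of the problem also depends on an unstated SD: at correlation 0.75 it nearly vanishes, and 25% is the peak of the curve at SD 1.6.

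The reply does not remove the gap. The summary does state a hypothesis and ties a practical decision to it, and nothing connects that hypothesis to the interval or to the 1 point. Even a narrow interval needs a number for what counts as major.

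**Conclusion.** The point holds as a missing link between hypothesis and analysis, and should be fixed. The stated test cannot by itself support the stated hypothesis. The quantities that could do so, the CI and the 1-point difference, are already in the plan but unused for that purpose.

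If the SD of differences is 1.6, the ambiguous result occurs in about 7% of trials when the true benefit is 0 or 1 and 25% when it is 0.5. Over correlations from 0.75 to 0 the range is under 1% to 57%. The upper end should not be taken as the expected size, because it belongs to an SD that does not fit the planned 30.

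A reader might conclude that the trial is too small for its hypothesis. The documents do not support that as a general statement. For no major benefit with a 1-point margin, 30 patients are enough at SD 1.6. They fall short of 90% power if the whole 95% CI must lie within ±1, or if the SD of differences is clearly larger.

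How the five boxes ("select a box from None, Mild, Moderate, Severe, to Extreme") are turned into a score is a separate issue and adds no weight here, though a margin in points presupposes a scoring.

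**What to change.** Add to the Statistics and Analysis section, before data are seen:

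- No major benefit of the lens on pain will be concluded only if the upper 95% limit of control eye minus lens eye is below a stated margin. The plan's own 1-point difference is the default, for the sponsor to justify.
- A non-significant result with an upper limit at or above the margin is inconclusive, and will not be described as showing that the lens is unneeded.
- The lower limit is reported alongside, since it shows whether the lens eye may have more pain.
- Power for this conclusion at zero true difference is stated as conditional on the SD of differences: with a 1-point margin, about 91% at 1.6 and 65% at 2.26.

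Limit the wording of the claim to no major benefit. If the sponsor keeps no major impact in both directions and requires the whole 95% CI within ±1, the plan should state the lower power of about 82% with 30 patients at SD 1.6.

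The cost is a few sentences, with no new data or analysis. The downside is that some results must be called inconclusive (about 25% at SD 1.6 and a true benefit of 0.5), and a margin below 1 point would lower the power. The rule covers pain only. Blurred vision, which the Project Summary also brings into the decision, is not settled by it.

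### A balanced right/left list with a side-adjusted comparison would cheaply protect the paired t-test against any right-left difference; the planned test is already valid

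*Combined protocol and SAP*

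**What the plan says.** Under Design and Procedure in the Methods, the unit of allocation is the side that keeps the lens: "Investigator will randomly generate for each patient whether the contact lens will be kept on right or left eye". The mechanism is unrestricted: "Randomization of the lens placement will be determined by a flip of a coin". No blocking, stratification or target split is described.

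Under Statistics and Analysis, the primary comparison is "Paired t-test will be used to compare the pain score between control and experimental eye", and the "mean difference with 95% confidence interval will be reported as treatment effect". No side term, stratum or sensitivity analysis by side is planned. The sample size is 30 patients, each contributing a lens eye and a control eye, chosen "to detect a mean difference of one score in pain with beta of 0.1 (90% power) and alpha of 0.05". Its starting point is this: "Assuming a mean pain score of 3.5 with standard deviation of 1.6 for control treatment".

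The documents give no evidence of a right-left difference in discomfort. They do not say which eyelid is operated on first, whether that order is fixed, or whether it is recorded.

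**The concern.** The coin creates two groups, lens-right and lens-left, much like the two sequences of a crossover trial. Let D be any systematic right-minus-left difference in pain that is unrelated to the lens. The lens-minus-control difference then has mean (effect + D) in the lens-right group and (effect - D) in the lens-left group. A plain paired t-test pools the two groups as if D were zero. Two things follow:

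- The spread between the groups enters the error variance.
- When the groups are unequal in size, part of D enters the estimate in that particular trial.

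This deserves attention here because the Project Summary expects no major effect of the lens and would use such a result to argue against routine use. That conclusion would rest on the position and width of one interval from 30 pairs. The randomisation already creates the grouping needed to remove both effects.

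**Working it through.** **Inputs.** From Statistics and Analysis: 30 pairs, target difference 1 point, alpha 0.05, power 90%, SD 1.6. From Methods: one fair flip per patient. Assumed: a two-sided test; 1.6 read as the SD of the paired difference within a side group; D between 0 and 1 point.

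**1. The plan's own figure.** With SD of differences 1.6 and a difference of 1, the noncentral t distribution gives 90.1% power at n = 29 and 91.1% at n = 30. The stated 30 is reproduced under that reading of 1.6.

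**2. How uneven the split can be.** With X ~ Binomial(30, 0.5):
- P(15:15) = 14.4%
- P(18:12 or worse) = 36.2%
- P(19:11 or worse) = 20.0%
- P(20:10 or worse) = 9.9%

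**3. Noise.** Over the coin flips, the SD of the differences is sqrt(1.6² + D²). The half-width is t(0.975, 29) × SD/sqrt(30), with t = 2.045.

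| D | SD | Planned power | CI half-width |
|---|---|---|---|
| 0 | 1.60 | 91.1% | 0.60 |
| 0.25 | 1.62 | 90.5% | 0.60 |
| 0.5 | 1.68 | 88.4% | 0.63 |
| 1 | 1.89 | 80.1% | 0.70 |

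Simulation (200,000 trials per scenario) agrees: 91.2%, 90.5%, 88.3% and 80.2%.

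**4. Shift in a given trial.** The shift is D × (nR - nL)/30. At 20:10 it is D × 10/30 = D/3, that is 0.08, 0.17 and 0.33 points for D = 0.25, 0.5 and 1. At 18:12 it is D × 6/30 = D/5, that is 0.05, 0.10 and 0.20.

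**5. Error rate of the planned test.** Averaged over the flips, simulated type I error is 5.0% for every D and the mean estimate under the null is 0.00. Conditional on a 20:10 split it is 5.7%, 7.5% and 11.9% for D = 0.25, 0.5 and 1. Conditional on 15:15 it is 4.7%, 4.1% and 2.0%. A balanced list alone therefore removes the shift but leaves the plain test conservative.

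**6. Side-adjusted comparison.** The estimate is (mean in lens-right + mean in lens-left)/2. Its standard error is (s/2) × sqrt(1/nR + 1/nL), where s is the pooled within-group SD on 28 df. Power does not depend on D:
- 15:15: 91.05% (planned test at D = 0: 91.12%); half-width 0.598 against 0.597
- 18:12: 89.9%
- 20:10: 87.6%; variance factor (1/4)(1/20 + 1/10) = 0.0375 against 1/30 = 0.0333, ratio 1.125

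**7. Side term with the coin kept.** Weighting the adjusted power by the binomial probability of each split gives an average of 90.0%. The planned test falls to 90.0% at D of about 0.32, where its SD is sqrt(2.56 + 0.32²) = 1.63. Below that D, adjustment with the coin loses power.

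**The case against.** The strongest reply is that nothing is wrong with the planned analysis. Side is randomised by a fair coin, so D averages out, the test keeps its nominal level, and what remains is chance imbalance of the kind found in any unadjusted randomised comparison. That stands. A reader might infer that the paired t-test is biased, that a side difference would systematically pass for a lens effect, or that the coin is itself unbalanced. The documents support none of these: allocation is 1:1 and merely unrestricted, and step 5 shows an unbiased test at 5.0%.

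It is also fair to say that D is hypothetical. No right-left difference or operating order appears anywhere in the plan, so an effect of operating first or second is only a possibility. The one scenario with a material loss needs D = 1, as large as the whole target effect. At 0.5 or less the loss is under 3 points of power. If the SD of differences were nearer 1.0 (an assumption), D = 0.5 would raise the variance by 25%, yet power would still be 99.7%, against 99.96% at D = 0. The half-width would go from 0.37 to 0.42.

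Finally, the sample-size sentence holds a larger uncertainty. It gives 1.6 for the control treatment, whereas 30 pairs needs 1.6 as the SD of the difference, which implies a between-eye correlation of 0.5 if 1.6 is the per-eye SD and both eyes share it. On the same footing power is 77% at correlation 0.25 and 65% at zero. That is a separate point, but it puts this one in proportion.

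What survives is narrower: the protection costs almost nothing if the list and the adjustment are adopted together.

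**Conclusion.** The point holds as a low-cost gain in efficiency and robustness, not as a flaw in validity. The gain depends on a D that the documents do not give: nil at D = 0, about 2.6 points of power at 0.5 (88.4% to 91.0%) and about 11 points at 1 (80.1% to 91.0%). These comparisons set the planned test with the coin against the adjusted test at 15:15. They rest on an SD of differences of 1.6, a true effect of 1 point and a two-sided 5% test. The main benefit beyond power is that a chance right/left imbalance would no longer be mixed into the one estimate that the trial produces. The sample size of 30 need not change on this account.

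**What to change.** Make both changes together, before enrolment starts.

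1. **Methods, Design and Procedure.** Replace the coin with a prepared random list holding 15 lens-right and 15 lens-left assignments, in blocks of varying size.
2. **Statistics and Analysis.** Replace the plain paired t-test for pain with the side-adjusted paired comparison: take the mean lens-minus-control difference in each of the two groups, average the two with equal weight, and report that estimate with its 95% CI and p-value on 28 df. Regressing the difference on a side indicator coded +1/-1 gives the same result.

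Do not add the side term while keeping the coin (step 7). If the coin must stay, keep the planned test as primary and report the side-adjusted result as a sensitivity analysis.

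Operating order can be recorded and examined in a sensitivity analysis. The primary model should not switch from side to order according to how order turns out, because the model would then be chosen after the fact. A list balanced on side does not balance order if order varies.

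The cost is one prepared list, one sentence in the analysis section and one degree of freedom: under 0.1 point of power at D = 0, and a half-width of 0.598 instead of 0.597.

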### **Ethics**

Informed consent will be obtained from patients by the staff Ophthalmologists and the consent form will be signed by the patient. In terms of any risks to the patient, the intervention being studied is currently the standard of care for many clinicians. Thus, participants in this study are not being exposed to any additional risk at all as a result of this study. The only risks faced by participants are those risks inherent to the surgical procedure that they will consent to undergo and these risks are the same for the treatment and control group.

### **Timescale**

This project is ready to begin as soon as possible and will be conducted for 6 months.

